5.1.1 Study Period

The trial consists of three periods: (1) the pre-transplant period, which includes screening, enrollment, and wait list time; (2) the period that includes the islet transplant procedure(s); and (3) follow-up visits through 24 months following the last transplant. The study period of this trial is a 36-month follow-up after the final islet transplant. Subjects may undergo up to 3 transplants in the course of this study; the last transplant can occur not later than 8 months following the first transplant.

In the first period, individuals who meet the general inclusion criteria will be approached regarding participation in the study. After informed consent has been obtained, they will be formally enrolled into the study. Eligibility will be confirmed based on the results of the screening visit procedure detailed in Appendix 1 of the CIT-06 protocol. Enrolled subjects who meet the eligibility screening for the studies will be put on the waiting list for an islet transplant.

After completion of the screening assessments confirming eligibility for the study, a subject will undergo 12 months of intensive insulin therapy (IIT) by an experienced diabetologist (see Appendix 3). If a subject received at least 12 months of **intensive diabetes management** prior to enrollment and experienced at least one episode of **severe hypoglycemia** during that time, the subject would not be required to receive IIT while on study as long as they have a Clarke score of 4 or more. A subject is required to return to the study site for clinic visits every 3 months while undergoing IIT and while on the waitlist. Monthly HbA1c sampling between the required 3 month interval visits may be drawn locally, sent from the local lab to the study site and then shipped to the central lab for testing. Eligibility will be reconfirmed after 4 months of IIT and after 12 months of IIT. All eligibility assessments must be within the windows required for initial study enrollment. Once eligibility has been reconfirmed, a subject will be placed on the **wait list**. The subject will continue IIT while on the **wait list**.

Once a compatible islet preparation becomes available, a subject's eligibility will be re-confirmed and eligible subjects will begin immunosuppression therapy on Day -2 (Day 0 is defined as the day of transplant).

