During the post-transplant follow-up period, subjects may receive up to two additional transplants. After receiving his/her first islet transplant, if a subject does not meet the criteria for insulin independence described in Study Definitions in the CIT-06 protocol, but has either a basal or stimulated C-peptide level ≥ 0.3 ng/mL (0.1 nmol/L), s/he will be considered for a second islet transplant. A subject who does not meet this criterion will be considered a transplant failure. A second islet transplant will be considered at 30 days but before 8 months after the first islet transplant and when all required metabolic assessments are complete. If, after the second islet transplant, both basal and stimulated C-peptide levels remain <0.3 ng/mL (0.1 nmol/L), the

Statistical Analysis Plan

recipient will be considered to have failed the endpoint, and immunosuppression will be managed as described in the protocol. A third islet transplant will be considered only if all the criteria described in Section 7.6 of the CIT-06 protocol are met. Islet transplant recipients who have completed 8 months of follow up after their first infusion will no longer be eligible for additional islet transplants under the CIT-06 protocol.

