5.1.2 Visit Windows

The number of visits that occur before the first islet transplant will be determined by time on the waiting list and cannot be determined in advance. Screening tests and baseline measurements that are obtained during this period must be obtained within specified windows relative to the day induction immunosuppression is initiated, as described in Appendix 1 of the CIT-06 protocol (section 7). Following each transplant, up to 23 visits may be scheduled. Subsequent transplants restart the clock at day 0. Table 4.1 describes all visits, their scheduled times relative to the islet transplant, and the allowable visit windows.

Table 4.1 - Study assessment time points and visit windows

Time Points (days relative to transplant)	Visit Number	Visit Window (days around target)	Equivalent (weeks or months)
Screening	01	N/A	N/A
IIT \geq 12 months	02		
Waitlist/Baseline	03	N/A	N/A
Baseline	04		
0	05	N/A	N/A
3	06	N/A	N/A
7	07	± 3	W1
14	08	± 3	W2
21	09	± 3	W3
28	10	± 3	W4
56	11	± 7	M2

Statistical Analysis Plan

Time Points (days relative to transplant)	Visit Number	Visit Window (days around target)	Equivalent (weeks or months)
75	12	±5	M2.5
180	13	±7	M6
270	14	±14	M9
365 after most recent transplant	15	±14	M12
Y1 365 days after first transplant	Y1	±14	M9
M 15	16	±14	M15
M 18	17	±14	M18
M 21	18	±14	M21
M24 after most recent transplant	19	±14	M24
Y2 730 days after first transplant	Y 2	±90	Y2 After first transplant
M27	20	±14	M27
M30	21	±14	M30
M33	22	±14	M33
M36 after most recent transplant	23	±14	M36
Y3 1095 days after first transplant	Y 3	±90	Y3 After first transplant

Statistical Analysis Plan

This follow-up schedule will restart with visit 05 on the day that a subsequent islet transplant is performed. Yearly visits occur after the first transplant. The detailed activities for each scheduled follow-up visit are described in Appendix 1 of the CIT-06 protocol.

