12.3.1 Analysis for SF-36 survey

Separate analyses for the SPC and SMC scales for each time point. Each composite score and their change from baseline values will be analyzed using the methods described for continuous variables.

In addition, we will perform the following longitudinal analyses. For each subject, we will include his/her score at baseline, 75±5, 365±14 days, 730±14 days, and 1095 ±14 days following the last islet transplant. We will use the linear mixed models with a term for time (baseline, 75 days, 365, 730, and 1095 days following the last islet transplant) and repeated measures on subjects.

The Shapiro-Wilk test is applied to test the hypothesis that the QOL scores are normally distributed. If the normality hypothesis is not rejected at significance level 0.05, a linear mixed model analysis will be performed using the observed test scores to test whether the mean QOL score is the same among the five time points. The results would be treated as follows:

- If the p-value for time is greater than 0.05, we conclude that there is no evidence to claim that QOL is changing over time.
- If the p-value is less than 0.05, we would compute the overall 95% confidence intervals for the pair-wise differences in the QOL score.

If the normality hypothesis is rejected at significance level 0.05, we will use the bootstrap procedure (sampling subjects with replacement) to construct the overall 95% confidence intervals for the pair-wise difference in the QOL score between any two time points. We will use the Benjamini and Hochberg (Benjamini & Hochberg, 1995) adjustment for multiple tests.

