- 90-minute MMTT glucose (measured quarterly year 1 post-first transplant, quarterly years 1, 2, and 3 post-last transplant)
- Basal c-peptide (measured quarterly year 1 post-first transplant, quarterly years 1, 2, and 3 post-last transplant)
- 90-minute MMTT c-peptide (measured quarterly year 1 post-first transplant, quarterly years 1, 2, and 3 post-last transplant)
- C-peptide/(glucose*creatinine) ratio (measured monthly year 1 post-first transplant and post-last transplant, then quarterly post-last transplant)
- Serum creatinine (measured monthly year 1 post-first transplant and post-last transplant, then quarterly post-last transplant)
- Atherogenic profile (measured year 1 post-first transplant and yearly post-last transplant)
- Quality of Life measures (measured day 75, day 180, yearly post-first and post-last transplant)
- Carotid IMT (measured year 1 post-first transplant and yearly post-last transplant)

Data analyses will be based on change from baseline for each variable. Data analysis will use linear mixed models to describe the profiles of change across time while accounting for correlation within subjects. We will use two strategies. The first strategy will select specific time points where data are routinely measured (e.g. 1 year after first transplant, and 2 and 3 years after last transplant). Estimates of mean change from baseline at these specific time points and 95% confidence intervals will be reported. Contrasts will be used to compare mean changes among time points. We will use the method of Benjamini and Hochberg (Benjamini & Hochberg, 1995)

Statistical Analysis Plan

to account for the multiplicity of comparisons. Next, we will fit polynomial regression models to describe the profile of mean change with time. Data will be displayed graphically and parameter estimates and confidence intervals for regression parameters will be reported. We will use the multiple imputations method to determine the potential effect of missing data.

13.2 Comparison of time profiles of eligible subjects who are transplanted with eligible subjects who are not transplanted

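### The example time points in SAP Section 13.1 mix the first-transplant and last-transplant clocks, so contrasts among them confound change over time with a change of time zero in re-transplanted subjects

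*SAP*

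**What the plan says.** Section 13.1 (Change from baseline) lists insulin requirement, HbA1c, Clarke score, β-score, glucose and C-peptide measures, serum creatinine, atherogenic profile, QOL and carotid IMT. Its first strategy picks routine measurement times, and the one set given is "e.g. 1 year after first transplant, and 2 and 3 years after last transplant". It continues: "Contrasts will be used to compare mean changes among time points", with a Benjamini-Hochberg adjustment. The second strategy follows: "Next, we will fit polynomial regression models to describe the profile of mean change with time". No time zero is given for it.

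Section 5.1.1 allows repeat infusions: "Subjects may undergo up to 3 transplants in the course of this study", and "the last transplant can occur not later than 8 months following the first transplant". It also gives the earliest repeat: "A second islet transplant will be considered at 30 days but before 8 months after the first islet transplant". Section 5.1.2 adds: "Subsequent transplants restart the clock at day 0".

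Other sections keep the clocks apart. Section 11 reports results after the first and after the last transplant separately. Section 12.3.1 models "his/her score at baseline, 75±5, 365±14 days, 730±14 days, and 1095 ±14 days following the last islet transplant". Section 12.4 repeats the whole time-to-event analysis for each time zero.

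**The concern.** The contrasts in Section 13.1 are the plan's tool for asking whether an outcome holds or drifts between years 1, 2 and 3. That question needs time points on one scale. In the named set, year 1 is counted from one event and years 2 and 3 from another. The two events differ only for subjects who had a further infusion. Under Section 5.1.1 these are subjects who were not insulin independent after the first infusion but still had measurable C-peptide. The shift of clock is therefore concentrated in a particular kind of subject.

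QOL shows the practical consequence. It is modelled on the last-transplant clock in Section 12.3.1 and is also on the Section 13.1 list. The same data could yield two different comparisons of year 1 with year 2. A polynomial fitted to times taken from both clocks would have the same fault.

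**Working it through.** The plan states no figure for this point, so there is none to reproduce. The check is clock arithmetic on target days, ignoring visit windows.

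**Inputs.** L is the lag from first to last transplant. It is 0 for a single transplant. Otherwise it runs from 30 days to 8 months (both from Section 5.1.1), and 8 × 365/12 = 243 days.

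**Formulas.**
- Days from last infusion to the visit 1 year after the first transplant: 365 − L
- Days from that visit to 2 years after the last transplant: (730 + L) − 365 = 365 + L
- Days from 2 to 3 years after the last transplant: 1095 − 730 = 365

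| L (days) | Year-1 value, days after last infusion | Year 1 to year 2 (days) | Excess over 365 | Year 2 to year 3 (days) |
|---|---|---|---|---|
| 0 | 365 | 365 | 0% | 365 |
| 30 | 335 | 395 | 8% | 365 |
| 122 (4 months) | 243 | 487 | 33% | 365 |
| 243 (8 months) | 122 | 608 | 67% | 365 |

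**Average step length.** The SAP does not give the share re-transplanted, f, so f is an assumption here. With L now the mean lag in months among those re-transplanted, the average first step is 12 + f × L months:
- L = 4: 13, 14 or 15 months for f = 25%, 50% or 75%
- L = 8 (the ceiling): 14, 16 or 18 months for the same shares

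**What the contrast estimates.** For complete data it splits exactly:

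(year 2 after last − year 1 after first) = (year 2 after last − year 1 after last) + (year 1 after last − year 1 after first)

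The first term is the one-clock change over 365 days. The second is the shift of clock. It is zero for single-transplant subjects, so averaged over everyone it equals f times its mean in the re-transplanted. Its sign depends on how the outcome moves between day 365 − L and day 365 after the last infusion, and the SAP says nothing about that.

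**Is a single clock feasible?** Every outcome on the Section 13.1 list has a scheduled measurement at year 1 after the last transplant, and at years 2 and 3 after it. With those points both steps are 365 days for every subject, whatever L is.

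**The case against.** The set is introduced as an example, so an analyst could choose otherwise. Section 13 is exploratory, and Section 10.2 says secondary outcomes are descriptive and do not decide efficacy. The example also has a rationale: the primary endpoint is read 1 year after the first transplant, and Section 2.4 lists the 2- and 3-year metabolic measures after the last one. Section 11 and Section 12.3 already give single-clock results for most of the outcomes.

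All of this stands, and it lowers the weight of the point. It does not remove it. The example is the only set named, nothing in Section 13.1 separates the clocks or adjusts for the lag, and an analyst following it would program the mixed contrasts. Serum creatinine, atherogenic profile and carotid IMT have no analysis in Section 11 to set beside them.

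A reader might go further and infer that graft or renal decline is overstated, perhaps by the same percentage as the interval is lengthened. The SAP does not support that. It would need an assumed linear decline common to all subjects, an assumed lag and an assumed share re-transplanted. If the outcome were still improving 122 days after a repeat infusion, the mixed contrast could understate later decline. Section 13.1 also compares mean changes at labelled time points and never defines a yearly rate that could be overstated.

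**Conclusion.** The point holds as a defect in the contrasts of an exploratory analysis. For each re-transplanted subject the first step is 8% to 67% longer than the second, and the year-1 value is read 30 to 243 days earlier relative to the last infusion than a year-1 value on the last-transplant clock would be. These figures follow from the SAP's own limits on the lag.

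The effect on any estimated contrast cannot be stated in size or direction. It is nil if nobody is re-transplanted or if the outcome is flat over the period concerned. Means at single time points are valid as labelled. Nothing in the primary or key secondary analyses depends on Section 13.1. The change is worth making because the named set would give a less interpretable answer than one the scheduled data already allow.

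**What to change.** In Section 13.1, replace the example with 1, 2 and 3 years after the last transplant for all listed outcomes, as Section 12.3.1 does, and take the contrasts among those points only. State the same time zero for the polynomial profile.

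Optionally repeat the contrasts at 1, 2 and 3 years after the first transplant, for whichever outcomes are measured at those visits, and report them as a separate set. This need not be confined to HbA1c and QOL, since Sections 2.3.2.2 and 11 plan further outcomes on that clock. The year-2 and year-3 visits after the first transplant carry ±90-day windows in the Section 5.1.2 visit table, so intervals there will be less exact.

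The cost is a change of SAP wording. No new visits or data are needed, because the 1-year values after the last transplant are already scheduled.

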8.2 Analysis of binary outcome variables

Binary outcome variables will be displayed as percents with 95% exact confidence intervals (Rosner, 1995). The exact confidence interval (P_L, P_U) will be as the solutions to the following equations. If x is the observed outcome (that is, there are x successes in the 24 subjects) then the lower bound will be the solution P_L to the equation

$$0.025 = \Pr \{ \text{at least } x \text{ successes} \mid \text{probability of success} = p_L \} = \sum_{k=x}^{24} \binom{24}{k} p_L^k (1-p_L)^{24-k}.$$

The upper bound will be the solution to the equation

$$0.025 = \Pr \{ \text{no more than } x \text{ successes} \mid \text{probability of success} = p_U \} = \sum_{k=0}^x \binom{24}{x} p_U^k (1 - p_U)^{24-k}.$$

Standard search methods will be used to solve these equations.

8.3 *Analysis of time to event measures*

All time to event measures will be summarized using Kaplan-Meier (product limit) life table methods. Results will be displayed as survival plots. Tables with estimates and 95% confidence intervals for the rates at 1-year, 2-years, and 3-years after the first and last islet transplants will be provided. Separate analyses will be performed for time from first transplant and time from last transplant.

9. Analysis of Demographic and Baseline Measures

9.1 *Baseline Data*

Baseline data collected for the ITT analysis consists of demographic information and medical/physical assessments during the waiting period for islet transplant. These data will be grouped into the following categories:

- Demographic variables
 - Age
 - Sex
 - Race (White, Black, Hispanic, Asian and Other)
- Body Habitus and Quality of Life
 - Body Weight
 - Height
 - Body Mass Index (BMI)
- Diabetes Control
 - Insulin requirement (units/day)
 - HbA1c
 - Fasting and post prandial plasma glucose
 - Fasting and post prandial C-peptide
 - 90-minute C-peptide following consumption of Boost[®] or equivalent
 - 90-minute glucose following consumption of Boost[®] or equivalent
 - Number of severe hypoglycemic events in the last year
 - MAGE score
 - LI
 - Clarke Score
 - HYPO score
 - β -score
 - C-peptide/(glucose·creatinine) ratio

Statistical Analysis Plan

- Measures of Cardiovascular function
 - Carotid intimal thickness
 - Atherogenic profile (fasting lipids, c-reactive protein, serum amyloid A, Apolipoprotein A1, Apolipoprotein B, and the ratio of Apolipoprotein A1 and Apolipoprotein B).
- Measures of Renal function
 - Serum Creatinine

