For each secondary outcome and time point where it is appropriate, we will compare transplanted subjects to those subjects who remain on intensive insulin therapy (IIT) but do not receive a transplant. Subjects can remain on IIT for up to one year so the time points and comparisons will be determined by the measures that are obtained while subjects are on wait list. Prior to transplantation, measures are obtained when subjects satisfy the IIT entry criteria (baseline) and either quarterly or every six months while subjects are on the waitlist. The proposed endpoints and time points are as follows:

- insulin requirements (measured every six months)
- HbA1c (measured months 3, 6, 9, 11, 12 encompassing the IIT and WL periods)
- MAGE (measured every six months)
- LI (measured every six months)
- Clarke Score (measured every six months)
- Hypo Score (measured every six months)
- Quality of Life measures (measured quarterly while on wait list)

Analysis will use the linear mixed model approach to describe and test for differences across the time points between transplanted subjects post-transplant and non-transplanted subjects while they are on wait list. Time zero will be defined as the day that the IIT criteria was satisfied for those who do not get a transplant and as the day of transplant for those that are transplanted. Because the two populations will be different at baseline, the analyses will need to adjust for the baseline value of the same outcome as well as age, gender, and baseline BMI. We will use the linear mixed models approach for these analyses. We will use models which treat time as a categorical variable. We will use a standard “factorial” design with terms for time, treatment (transplant or no transplant), and the interaction between time and treatment. If the interaction is significant (which we expect) then we will test for the difference between treatments at each time point. We will report means and 95% confidence intervals for the difference at each time point. We will use the method of Benjamini and Hochberg (Benjamini & Hochberg, 1995) to account for the multiplicity of tests.

13.3 Comparison of pre-transplant and post-transplant time profiles of subjects who are transplanted.

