For those who have been transplanted, we will compare the profiles of change over time while the subject was on waitlist to change over time after the subject has received a transplant. We begin collecting data pre-transplant when the subject becomes eligible for transplant. Time zero for the pre-transplant values will be when the subject becomes eligible for transplant. Time zero for post-transplant observations will be the day of transplant. The endpoints and times will be the same as those described in the previous section. Analysis will use the linear mixed model approach. The models will have terms for time, transplant status (pre-transplant or post-transplant), and the interaction between time and transplant status. If the interaction is significant (which we expect) then we will test for the pre-post difference at each time point. We will report means and 95% confidence intervals for the difference at each time point. We will use the method of Benjamini and Hochberg (Benjamini & Hochberg, 1995) to account for the multiplicity of tests.

14. Safety Analyses

Safety analyses will be conducted for the safety population. Summaries will be prepared for the targeted safety endpoints listed in the secondary endpoints and for all observed AEs organized by body system. The CIT consortium modified the National Cancer Institute (NCI) toxicity table to create a document relevant for trials of adult pancreatic islet transplantation. The resulting reference manual, “Terminology Criteria for Adverse Events (TCAE) In Trials of Adult Pancreatic Islet Transplantation,” provides descriptive terminology and a grading (severity) scale which will be utilized for adverse event (AE) reporting.

Regular safety analyses will be prepared for the Data Safety Monitoring Board (DSMB). These summaries will be used to monitor the overall safety profile of the study. These analyses will summarize all AE data that are available at the time of the DSMB meeting. Analyses will summarize AEs by MedDRA term and body system. Separate incidence summaries will be prepared for serious AEs, for nonserious AEs and for all AEs combined. Separate tables will summarize severity and attribution. Each AE can be attributed to the investigational agent (allogeneic islets), the immunosuppression, both or neither. Identical safety summaries will be included in the final statistical report.

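### Section 13.2 starts untransplanted subjects at entry to intensive insulin therapy and transplanted subjects at transplant, so the comparison mixes the insulin run-in with the transplant effect

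*SAP*

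**What the plan says.** Section 13.2 of the SAP sets two time origins in one sentence. For untransplanted subjects: "Time zero will be defined as the day that the IIT criteria was satisfied for those who do not get a transplant". For the others: "and as the day of transplant for those that are transplanted".

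The same section indicates what the first origin means: before transplantation, "measures are obtained when subjects satisfy the IIT entry criteria (baseline", and then quarterly or six-monthly. Its HbA1c schedule reads "HbA1c (measured months 3, 6, 9, 11, 12 encompassing the IIT and WL periods".

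Section 5.1.1 gives the sequence of therapy. After screening, "a subject will undergo 12 months of intensive insulin therapy (IIT) by an experienced diabetologist". Then: "Eligibility will be reconfirmed after 4 months of IIT and after 12 months of IIT". The subject is placed on the wait list only after that, and IIT carries on there. A subject with at least 12 months of earlier intensive management, a severe hypoglycemic episode in that time and a Clarke score of 4 or more is exempt from on-study IIT.

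For the treated (ITT) population, section 9.1 takes baseline from "medical/physical assessments during the waiting period for islet transplant". Section 12 uses the last wait-list value before transplant as the quality-of-life baseline.

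The 13.2 model is a linear mixed model with time, treatment and their interaction, adjusted for baseline outcome, age, gender and BMI. It has no term for time on IIT.

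**The concern.** A between-group comparison over time needs both groups to be at the same stage of background treatment at time zero. Here one clock starts as background therapy is intensified and the other starts a year or more later. Any change that IIT itself produces in its first year is counted as follow-up change in controls but as baseline in transplanted subjects.

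Section 13.2 is the SAP's only comparison with concurrent untransplanted subjects. It is to be reported with an interaction test, differences and confidence intervals at each time point, and a Benjamini-Hochberg adjustment. A reader could take those differences as transplant effects when they are confounded with stage of IIT.

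**Working it through.** **Step 1: the two clocks side by side.** These follow from sections 13.2 and 5.1.1, for a control who receives IIT on study.

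| | Untransplanted | Transplanted |
|---|---|---|
| Time zero | IIT entry criteria met | day of transplant |
| Time already on intensive therapy | about 0 months | 12 months or more |
| Baseline value | at IIT entry | during the waiting period |
| Months 0 to 12 contain | first year of IIT | second year of intensive therapy or later, plus transplant |

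**Step 2: what baseline adjustment does.** The SAP states no figure for this contrast, so there is none to reproduce. Let μ be mean HbA1c at IIT entry, d the fall over the first 12 months of IIT (then a plateau), τ the true transplant effect, and b the within-group slope of follow-up on baseline. At month 12:

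- Controls: baseline μ, follow-up μ − d.
- Transplanted: baseline μ − d, follow-up μ − d + τ.
- Adjusted difference = (difference in follow-up) − b × (difference in baseline) = τ − b × (−d) = τ + b·d.

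With both clocks started after 12 months of IIT, the two baselines are both μ − d and the adjusted difference is τ.

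**Step 3: numbers.** All inputs are assumptions: between-subject SD 1.2, within-subject SD 0.4, μ = 8.6. Then b = 1.2² / (1.2² + 0.4²) = 1.44 / 1.60 = 0.90. A simulation of the month-12 contrast (200 per group, 400 replicates) agrees. The value τ = −1.5 is borrowed from the mean change in Table 4.3 (16 subjects, before to after transplant) only to set a scale.

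| Assumed d | Formula bias 0.9d | Simulated estimate, τ = −1.5 | Simulated estimate, τ = 0 |
|---|---|---|---|
| 0 | 0 | −1.50 | 0.00 |
| 0.3 | 0.27 | −1.23 | +0.27 |
| 0.5 | 0.45 | −1.05 | +0.44 |
| 1.0 | 0.90 | −0.60 | +0.90 |

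As a share of 1.5 points, the bias runs from 0.27 / 1.5 = 18% to 0.90 / 1.5 = 60% over this range of d. With the clocks aligned, the simulation returned about −1.50 and 0.00 throughout. Exempt controls carry no on-study run-in, so the bias falls roughly in proportion to their share of the control group.

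**Step 4: internal consistency.** Section 13.2 says IIT can last no more than a year and describes controls as being on the wait list. Section 5.1.1 puts the reconfirmed wait list after 12 months of IIT and continues IIT during it. A programmer cannot satisfy both descriptions together with a month 3 to 12 HbA1c schedule that spans the IIT period.

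**Step 5: section 13.3.** There, "Time zero for the pre-transplant values will be when the subject becomes eligible for transplant". Under 5.1.1 eligibility is confirmed at screening, after 4 months, after 12 months and again when islets become available, so this date is not unique.

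**The case against.** The best defense is that section 13.2 twice refers to subjects on the wait list. If that is the reconfirmed list of 5.1.1, controls would already be past 12 months of IIT and the offset would largely vanish. This shows that the text is inconsistent, but it does not rescue it: the explicit time-zero sentence, the reference to entry criteria as baseline and the HbA1c schedule all point to IIT entry.

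Several stronger readings are tempting, and the document does not support them:

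- **A known or proven run-in.** Section 4 gives a 27% favorable rate under IIT (101/373 = 27.1%). That is a responder rate in subjects selected for HbA1c above 7.0% at months 3 and 4. It gives no mean change, so d remains an assumption.
- **Benefit hidden across all outcomes.** The direction follows only for outcomes that IIT improves, such as HbA1c. Section 4 notes that hypoglycemic events were common in the DCCT. If early IIT raises hypoglycemia, the bias in Clarke and HYPO could go the other way.
- **Exempt subjects make it worse.** They have already had at least 12 months of intensive management, so as controls they dilute the bias.
- **Wait-list time of later-transplanted subjects is thrown away.** Section 13.2 does not use it, but section 13.3 does.

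Reconfirmation of eligibility could also limit d, because strong HbA1c responders may cease to be eligible. The SAP does not say whether such subjects stay in the comparison.

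It also stands that section 13 is exploratory, that section 10.2 calls the secondary analyses descriptive, and that 13.2 itself concedes the two populations differ at baseline.

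**Conclusion.** The concern holds for section 13.2 as written. For controls on study IIT, the first 12 months of follow-up contain the run-in, and the planned covariates do not remove it. The HbA1c bias is roughly d against transplant, or about 0.9d under the assumed variances and a plateau after 12 months. The SAP does not supply d, so no actual size can be claimed, and the direction for the other outcomes is open. The time-zero wording also conflicts with section 5.1.1. This should be corrected before analysis, but it does not touch the primary or key secondary analyses.

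**What to change.** In section 13.2:

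- **Untransplanted subjects:** set time zero at wait-list entry, once eligibility is reconfirmed after 12 months of IIT. For IIT-exempt subjects, use the day they are wait-listed. Baseline is the last value before that day.
- **Transplanted subjects:** time zero is the day of first transplant, and baseline is the last value before induction.
- **If too few control values remain after wait-list entry:** keep the IIT-phase values only in a model that includes time since the start of IIT, and label the contrast as confounded by time on IIT.
- **Wording:** reconcile the statements on the duration of IIT and on wait-list status with section 5.1.1.

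In section 13.3, state that becoming eligible for transplant means the same wait-list entry date.

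The cost is SAP wording and programming on data already being collected. The real downside is fewer control observations, possibly very few for HbA1c, whose listed time points stop at month 12; the fallback model is there for that case. A redesign with transplant as a time-varying status is possible but is not needed to correct this fault.
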